text reminder will also be sent approximately 2 weeks before each follow-up data collection time point.

Study Conditions

Intervention:

Those in the intervention group will then be connected to 211LA via warm transfer phone call for care coordination, including a review of developmental screening responses and information about and connection to relevant developmental and behavioral evaluations and services. The care coordinator specialist will stay in touch with the family for 3-6 months or until the parent wishes to discontinue contact or the child is enrolled in services. The RA will also text a 211LA flyer and contact information to the parent. The RA will provide participant contact information (child and parent name, phone number, address) and basic demographic information (child age, race/ethnicity, language preference, education, income, insurance status, household size) to the care coordination specialist via an online encrypted WebForm hosted on 211LA's HIPAA compliant care coordination platform / database.

After connection to 211LA, the care coordination specialist will develop a care coordination plan – including referrals suggested for community agencies – and will fax this plan to the clinic. At the conclusion of care coordination, the care coordination specialist will provide the outcome of each referral, including services received and barriers faced. This data will also be transferred to the research team via encrypted electronic transfer on an ongoing basis – along with care coordination time investment per participant.

After baseline data collection, parents will receive a \$25 cash incentive to compensate them for their time. This incentive will be mailed to study participants along with a copy of their HIPAA authorization and a copy of the study information sheet.

Measures

Follow-up Data Collection:

Participants will be contacted 3 more times after baseline for study research data collection – 6 months, 12 months, and 24 months after baseline. Follow-up data collection will be very similar to baseline data collection and parents will receive \$15, \$25, and \$25 cash incentives to thank them for their time. For hard-to-reach participants, we will add a small additional incentive of \$10 dollars in value at any time point (6M, 12M, 24M).

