The 6-month survey includes the M-CHAT-R for children who were too young at baseline to receive the screening. No other developmental screenings will be administered at 6, 12, or 24 months. The Child Behavior Check List will be administered at 6, 12, and 24 months and the PEDS:DM-AL will be administered in the same fashion as baseline at 12 and 24 months, as will experiences with care and anticipatory guidance. At all follow-up time points, participants will be asked about referrals and connections to services and those in the intervention group will be asked about their experiences with 211 at 6 months. At each follow-up time point, the RA will call and text a study participant up to 20 times each (10 calls, 10 texts) to connect for the interview, unless otherwise specified by the family. We will contact by email study participants that we have already contacted by phone but haven't been able to reach to complete the follow-up surveys.

Chart Abstraction:

Medical record review will occur at baseline and throughout the study time period. The RA will conduct electronic health record reviews for each of the study participants. They will assess developmental surveillance, developmental screening (validated screening tool use), and documentation of referrals and services from birth to baseline as well as in the 24 months of the study period. After completing site-specific training and documentation, the RA will be provided with an administrative login for each site's electronic health / medical record. They will use this to log in to access the electronic medical record and review the study participant's record for the noted elements. In addition, the RA will review for process measures – including the attendance of the scheduled baseline well child check-up, upload of developmental screening results into the medical record, as well as upload of the care plan and care coordination outcome summary.

Statistical and Data Analysis Plan:

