Given that the intervention being tested requires parent adherence to recommendations (e.g., communicating with 211LA, keeping referral and service appointments) to achieve success, we will use an intention-to-treat analysis. Our analyses will be based on measuring differences between the intervention and comparison groups with respect to the above outcome variables. Additionally, covariate-adjusted differences will be evaluated using multivariable regression models. Incomplete variables will be handled using a multiple imputation approach with 10 imputations for multivariable analyses; imputations will be based on an iterative Markov chain Monte Carlo method, with initial values generated by an expectation–maximization algorithm. Finally, secondary analyses for all outcomes will include group*developmental screening risk category (low, moderate, high), or group*gender (female, male) interactions to explore differential intervention effects.

Hypothesis 1: A higher proportion of families in the intervention group will a) be successfully referred to early childhood service organizations for evaluation, and b) receive services, than families in the usual care group.

We will use multivariable logistic regression models for each of these binary outcome variables with group assignment as the main predictor, controlling for socio-demographic variables.

Secondary analyses will use the fact that multiple types of services may be indicated. This will allow us to examine specific services in isolation as binary outcome variables in logistic regressions. It is possible that certain types of services are more likely to be recommended or taken up than others. It is also possible that receipt of any vs. no services is too crude to distinguish among different types or severities of developmental needs. Thus, examining specific services may prove to be important adjunct analyses.

Hypothesis 2: Over time, formal developmental assessment scores in the intervention group will improve more than scores in the usual care group.

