In all children, linear regressions will be used to compare PEDS:DM-AL language subscale scores in each arm. In the subset of children who screened positive and therefore received the full PEDS:DM-AL (Parents' Evaluation of Developmental Status: Developmental Milestones - Assessment Level), linear regressions will be used to compare each of the subscale scores in each arm. Since we will have baseline and 2-year follow-up PEDS:DM-AL scores, we will use change from baseline scores as outcomes, allowing us to compare change in the intervention group against change in the comparison group.

We will also conduct exploratory secondary analyses, each with probative value but less certain power. Since we will have scores measured at baseline and 1-year and 2-year follow-ups, we will be able to conduct longitudinal analyses, with multiple observations clustered within individuals using linear mixed models with random child effects. These models will adjust for

socio-demographic variables. The outcome variables will be appropriately transformed prior to fitting the model as needed.

The mixed effects models described above allow us to make statistical inference using all observed data, with the assumption of data missing at random. To assess the robustness of this analysis with respect to missing data, multiple imputation with pattern mixture models will also be used to impute missing data due to missed visits or loss to follow-up. For example, as a sensitivity analysis, we will assume that the distribution of missing data from missed visits or loss to follow-up is similar with that of the usual care group.

Secondary outcomes will include CBCL, family-centered care, and satisfaction scores. We will conduct longitudinal analyses like those for the language subscales. Also, sensitivity analyses clustering children by provider will be performed to assess robustness of findings to potential contamination by provider.

Hypothesis 3: Intervention costs per child screened will be exceeded by the societal value of the long-term benefits from 211-based care coordination.

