We will compare costs per child screened to benefits. Total costs will be disaggregated into RA screening/initial referral, 211 program, and diagnostic and developmental services costs. Total benefits will be disaggregated into income and value of life expectancy gains. Using evidence from literature, these benefits will be estimated by predicting changes in educational achievement from improvements in early life assessments (Aim 2 findings), then predicting changes in educational attainment from changes in educational achievement, and then predicting changes in lifetime income and life expectancy from changes in educational attainment. Sensitivity analyses will explore alternative assumptions about costs, relationships between early-childhood development and long-term outcomes, and value of a life-year.

Power Analysis

Given our planned RCT enrollment of 662 families (331 per group), and assuming loss to follow-up of 20% per year, we expect 424 families (212 per group) to complete the study. For each hypothesis, we report minimally detectable differences using study completers. These estimates are likely conservative, since some analyses will be performed using data collected prior to the end of follow-up and including >424 families. The enrollment sample size was chosen so that detectable differences would be within the bounds of the confidence intervals from the pilot data. Unless otherwise noted, reference rates were estimated from the pilot study.

Hypothesis 1: A higher proportion of families in the intervention group will a) be successfully referred to early childhood service organizations for evaluation, b) be deemed eligible for services by service organizations, and c) receive services, than families in the usual care group.

a) A sample size of 212 per group provides 80% power to detect a 11.9 percentage-point difference in the referral rate, assuming a reference rate of 20.4%, a chi-squared test, and an alpha of 0.05. This difference is smaller than observed in the pilot study (21.8 percentage points; 95% CI: 9.1-33.8).

b) A sample size of 212 per group provides 80% power to detect an 9.2 percentage-point difference in the eligibility rate, assuming a reference rate of 8.6%, a chi-squared test, and an alpha of 0.05. This difference is smaller than observed in the pilot study (14.3 percentage points; 95% CI: 5.6-24.0).

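### Hypothesis 3 sets benefits to society against a cost total that does not list parent time, although the intervention depends on it and should increase it

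*Combined protocol and SAP*

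**What the plan says.** Under Hypothesis 3 in the Statistical and Data Analysis Plan, the claim to be examined is: "Intervention costs per child screened will be exceeded by the societal value of the long-term benefits from 211-based care coordination". The text below it sets out the two sides. For costs: "Total costs will be disaggregated into RA screening/initial referral, 211 program, and diagnostic and developmental services costs". For benefits: "Total benefits will be disaggregated into income and value of life expectancy gains". On uncertainty: "Sensitivity analyses will explore alternative assumptions about costs, relationships between early-childhood development and long-term outcomes, and value of a life-year". No costing perspective is stated for the cost side.

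Three other places bear on what families put in:

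- The opening paragraph of the same plan says that the intervention "requires parent adherence to recommendations (e.g., communicating with 211LA, keeping referral and service appointments) to achieve success".
- The Intervention section under Study Conditions says: "The care coordinator specialist will stay in touch with the family for 3-6 months", unless the parent ends contact or the child is enrolled in services sooner. It also says that 211LA sends the research team the outcome of each referral "along with care coordination time investment per participant".
- Follow-up Data Collection under Measures says: "At all follow-up time points, participants will be asked about referrals and connections to services". No question on parent time, travel or lost work is described there or in the baseline survey.

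**The concern.** Benefits are valued for society as a whole, and income and longer life go largely to the child and family. The cost breakdown is given as a division of the total, not as a list of examples, and it has no entry for the time parents spend. The plan itself treats that time as a necessary input.

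The input also differs between arms. If Hypothesis 1 is right, intervention families attend more evaluations and services than usual-care families, and they also spend time with the coordinator. The missing cost therefore does not cancel in the comparison, and it grows with each additional family connected. At stake is whether a finding that benefits exceed costs can be read as a statement about society, or only about programme and service spending.

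**Working it through.** **Is there a figure to reproduce?** No. The documents give no cost, benefit, ratio or power figure for Hypothesis 3. The only planning figure borrowed below for scale is the detectable difference in service receipt in the Power Analysis: 8.7 points over 7.2%, with 212 per group. A two-sided 0.05 test of 7.2% against 15.9% without continuity correction has power 0.802, so the stated 80% reproduces.

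**The two sides compared**

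| | Listed in the plan | Parent time listed? |
|---|---|---|
| Costs | RA screening/initial referral; 211 program; diagnostic and developmental services | No |
| Benefits | Income; value of life expectancy gains | Not applicable |
| Sensitivity analyses | Costs in general; development-to-outcome links; value of a life-year | Not named |

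**Direction of the omitted item.** Let Δp be the extra share of children receiving services in the intervention arm, H the parent hours per served child, and w the value of an hour. The omitted incremental cost per intervention-arm child is at least

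Δp × H × w.

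Hypothesis 1 predicts Δp > 0, and H and w are positive. The term is therefore positive and rises in proportion to Δp.

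**Illustrative size.** Δp comes from the Power Analysis: 8.7 points (detectable) and 11.7 points (pilot; 95% CI 3.4-21.0). H and w are not in the documents. I assume H = 20-200 hours and w = $15-30.

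- Δp = 0.087: 0.087 × 20 × 15 = $26, up to 0.087 × 200 × 30 = $522.
- Δp = 0.117: 0.117 × 20 × 15 = $35, up to 0.117 × 200 × 30 = $702.

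One case inside that range of hours makes the visit count explicit. Assume 52 visits, 2-3 hours each and $15-25 per hour.

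- Per served child: 52 × 2 × 15 = $1,560, up to 52 × 3 × 25 = $3,900.
- Times 0.117: $183 to $456 per intervention-arm child.
- Across the pilot interval: 1,560 × 0.034 = $53, up to 3,900 × 0.21 = $819.

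The visit count drives this second set as much as the hourly value does, and it too is an assumption. Neither set includes time with 211LA, evaluations of children who go on to receive no services, or travel.

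**Data available to cost it.** The plan describes referrals and service connections by survey and chart abstraction in both arms, and coordinator time from 211LA in the intervention arm. It describes no visit counts. Coordinator time is not parent time, since it may include work done without the parent, such as preparing and faxing the care plan.

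**The case against.** The strongest reply is that the benefit side is narrow too. Only income and life expectancy are counted, although the Objectives in the Abstract speak of educational, employment and other outcomes. Leaving out other benefits works against Hypothesis 3. A reader might infer that the analysis as a whole is biased toward finding that benefits exceed costs. The documents do not support that: the missing cost and any missing benefits pull in opposite directions, and neither is quantified. What stands is the narrower statement about the cost side, all else equal. A possible missing benefit is no reason to leave out an input the plan calls necessary.

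Second, the sensitivity analyses are to cover alternative assumptions about costs, and nothing in that wording excludes family costs. This is fair: the plan is silent and does not rule them out. But it does not name them, and the base case would still lack them.

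Third, a reader might infer that families bear costs of which nothing is counted. The documents do not say who pays for diagnostic and developmental services, so family out-of-pocket payments could already fall within that component. Nor do they mention travel. Coordination is by telephone and service settings are not described, so travel is only an inference from keeping appointments. Parent time does not rest on that inference.

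Finally, Hypothesis 3 is a modelling exercise with several literature-based links, its cost scope is disclosed, and the word societal is attached to the benefits. This limits the importance of the point. It does not explain why the two sides have different scopes.

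**Conclusion.** The point holds in a limited form. As written, the cost total omits parent time that the plan says the intervention requires and that Hypothesis 1 implies will be greater in the intervention arm. All else equal, incremental societal cost is understated, and by more the better the intervention works.

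The size cannot be computed from the documents. On the assumed inputs it runs from tens to several hundred dollars per child. With no benefit or cost total to set this against, whether the conclusion on Hypothesis 3 would change cannot be determined, and the figures should not be read as showing that it would. The net bias of the full comparison is likewise not established. Hypotheses 1 and 2 are unaffected. This is a worthwhile, inexpensive improvement to the economic analysis.

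**What to change.** In the text under Hypothesis 3, state a societal perspective for both sides. Add parent time, and travel where services are in person, as a named cost component. Calculate it as the intervention-minus-usual-care difference from the referral, service and 211LA contact data already collected. Take service use from the survey and chart sources that exist in both arms, and treat coordinator time only as a guide to parent time on calls. State visit counts, hours per visit and hourly value as assumptions, vary all three in the sensitivity analyses, and report net benefit with and without the component.

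If parent time is not included, say that the cost side covers programme and service costs only, and word the conclusion so that it does not claim net societal benefit. Deleting the word societal from the hypothesis would not be enough: lifetime income and life expectancy would remain as the benefits, and those are not returns to the programme.

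The cost is a short edit to the plan and a few more model inputs, with no new data collection essential. The downside is that three inputs are assumed rather than measured, and net benefit becomes somewhat less favourable.

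### Hypothesis 3 does not carry the sampling error of the Aim 2 effect into net benefit, so benefits above costs could be reported when the developmental effect is compatible with zero

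*Combined protocol and SAP*

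**What the plan says.** In the Statistical and Data Analysis Plan, Hypothesis 3 is directional: "Intervention costs per child screened will be exceeded by the societal value of the long-term benefits from 211-based care coordination". The stated method is a direct comparison: "We will compare costs per child screened to benefits".

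Benefits are income and life-expectancy gains. They are reached by a chain that starts from the trial and continues with links from the literature: "these benefits will be estimated by predicting changes in educational achievement from improvements in early life assessments (Aim 2 findings". Later links run from achievement to attainment, and from attainment to income and life expectancy.

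On the cost side, "Total costs will be disaggregated into RA screening/initial referral, 211 program, and diagnostic and developmental services costs". Under Study Conditions, Intervention, the 211LA data passed to the research team come "along with care coordination time investment per participant".

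Uncertainty is covered by one sentence: "Sensitivity analyses will explore alternative assumptions about costs, relationships between early-childhood development and long-term outcomes, and value of a life-year".

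The Aim 2 effect itself is defined under Hypothesis 2: "we will use change from baseline scores as outcomes, allowing us to compare change in the intervention group against change in the comparison group". The Power Analysis section announces detectable differences for each hypothesis but gives none for Hypothesis 3.

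**The concern.** The Aim 2 effect is the only trial-estimated quantity at the head of the benefit chain, and its random error is the part of the uncertainty that the trial's own data can measure. The listed sensitivity analyses vary cost assumptions, the links between early development and later outcomes, and the value placed on a life-year. None of these varies the between-arm effect. The mixed models, multiple imputation and pattern-mixture analyses described earlier in the plan serve the outcome analyses and are not tied to Hypothesis 3. Nor does the projection depend on what Aim 2 shows.

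At stake is the wording of a conclusion. A positive but imprecise developmental effect, multiplied forward over a lifetime, can yield a projected benefit larger than cost. The reader of that comparison would see ranges for the assumptions but no statement of how well the trial supports the effect beneath them.

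**Working it through.** **Inputs from the Power Analysis section**
- 662 families, 331 per group, with 20% lost per year: 662 × 0.8 × 0.8 = 423.7, or 424 completers (212 per group).
- Hypothesis 2: 80% power for an effect size of 0.27, two-sample t-test, two-sided alpha 0.05.

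**Step 1. Reproduce the plan's figure.** Minimum detectable effect = (1.960 + 0.842) × sqrt(2/212) = 0.272 (0.273 with the t distribution), which rounds to 0.27. Power at 0.27 is 79.4% (normal) or 79.2% (t). The figure reproduces.

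**Step 2. Sampling error of the effect that feeds Hypothesis 3.** SE = sqrt(2/212) = 0.097 SD. The 95% half-width is 1.96 × 0.097 = 0.19 SD. This takes the effect as standardised on the analysed score, with no covariate adjustment.

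| Observed effect (SD) | 95% interval |
|---|---|
| 0.10 (illustrative) | -0.09 to 0.29 |
| 0.15 (illustrative) | -0.04 to 0.34 |
| 0.27 (design effect) | 0.08 to 0.46 |

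Any positive estimate below about 0.19 SD has an interval that includes zero.

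**Step 3. How often this would arise.** The chance that the estimate is positive but not significant is 47.5% if the true effect is 0, 67% if it is 0.10, 60% if 0.15 and 20% if 0.27.

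**Step 4. Effect on the cost comparison.** Net benefit cannot be computed, because the documents give no costs, benefit values or break-even effect. As an assumption, let break-even range from 0.01 to 0.19 SD. If the true effect is zero, the chance that the estimate lies above break-even and is still non-significant is:

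| Assumed break-even (SD) | Chance |
|---|---|
| 0.01 | 43% |
| 0.05 | 28% |
| 0.10 | 13% |
| 0.15 | 4% |
| 0.19 | about 0% |

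**Step 5. Sensitivity to sample size.**
- The Methods section gives a recruitment target of 685 rather than 662. 685 × 0.64 = 438 completers (219 per group) gives a half-width of 0.187.
- No loss at all (331 per group) gives 0.152.
- Most PEDS:DM-AL subscales are given only to moderate- and high-risk children, and the documents do not state their number. If an assumed 25%, 40% or 60% of completers are in that subset (53, 85 or 127 per group), the half-width is 0.38, 0.30 or 0.25 SD. The plan does not say which scores feed Hypothesis 3.

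**The case against.** The strongest reply is that the plan is silent rather than wrong. It does not forbid an interval, and a null developmental effect would be visible in the Hypothesis 2 result. That is fair as to intent. But nothing links the Hypothesis 2 interval to the Hypothesis 3 conclusion, and the uncertainty work that is specified leaves out the effect on which every benefit depends. The omission stands.

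Second, 0.10 SD is a chosen value. It is below the 0.27 SD design effect and below the 0.3 lower end of the cited meta-analyses, and at 0.27 the interval excludes zero. This is why 0.10 is only an illustration; the 0.19 SD threshold does not depend on it. Small average effects are also plausible on the plan's own figures. If benefit came only through extra service receipt (an assumption), the pilot difference of 11.7 percentage points and the cited speech and language effects of 0.3 to 0.8 imply an average over all children of 0.117 × 0.3 = 0.035 to 0.117 × 0.8 = 0.094 SD.

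Third, a reader might infer that sampling error is ignored for all costs. The documents do not support that. Cost assumptions are varied, and the only cost input clearly recorded per participant is 211 coordination time. Screening and service costs may be built from unit costs; the plan does not say.

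A reader might also infer that the planned ranges are error bars that are too narrow. The plan states no error bars, and scenario ranges are not confidence intervals. Without figures, nobody can say whether the trial's sampling error or the literature links would dominate.

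**Conclusion.** The point holds as an omission with a practical consequence. As written, Hypothesis 3 could report benefits above costs when the Aim 2 effect is compatible with zero, and the reader would not be told so in that comparison. The threshold is about 0.19 SD, on 212 completers per group and an unadjusted standardised effect.

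The consequence is conditional. It depends on the break-even effect, which the documents do not give, and it largely disappears if break-even is about 0.19 SD or more. A reader might go further and state how many times larger or smaller the benefits could be. That would need a linear benefit chain and a particular point estimate, and the plan gives no functional form. Nor do the documents require that Hypothesis 3 be accepted only if the net-benefit interval excludes zero: no alpha is assigned to this modelled comparison.

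Hypotheses 1 and 2, the randomisation and the sample size are unaffected. The change is worth making because Hypothesis 3 is stated as a hypothesis and the needed information will be in hand.

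**What to change.** Amend the Hypothesis 3 section of the analysis plan as follows.

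- Carry the Aim 2 sampling error into net benefit, jointly with costs measured per participant (such as 211 coordination time). Either bootstrap children within arm and randomisation strata, re-estimating effect and cost in each sample, or run a probabilistic sensitivity analysis that draws both from their joint sampling distribution.
- State how this combines with the planned 10-fold multiple imputation, for example whether imputation is repeated within each bootstrap sample or resampling is done within each imputed data set.
- Name the PEDS:DM-AL score or scores, and the population, that feed the projection.
- Draw the literature links from their reported errors where these exist; otherwise vary them over a stated range.
- Report net benefit with a 95% interval and the probability that it exceeds zero. Keep the scenario analyses as an addition.
- Say in advance that the Hypothesis 3 conclusion will be worded to reflect that interval, including when the Aim 2 interval includes zero. A strict rule that the interval must exclude zero is optional.

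No new data are needed. The cost is plan wording and extra programming, most of it in joining resampling to imputation and in assembling errors for the literature links. The Hypothesis 3 result will also look less certain.
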